13.5 Anaphylaxis

A suspicion of anaphylaxis will be carefully monitored and treated according to standard of care. Emergency crash cart equipment and medications, including multiple doses of epinephrine, vasopressors, and bronchodilators, will be available at all times during the conduct of the study. To define anaphylactic reactions in a consistent and objective manner, all events of suspected anaphylaxis will be evaluated using Sampson's Criteria for Anaphylaxis ([Appendix 7](#)). The assessment of an AE will be done pursuant to definitions set forth by ICH Good Clinical Practice (GCP) guidelines and applicable regulatory requirements.

If a patient experiences signs or symptoms of anaphylaxis, the patient may be treated with standard of care, such as diphenhydramine, acetaminophen, methylprednisolone, epinephrine, and other supportive measures along with cessation of the infusion.

13.6 Evaluating Adverse Events and Serious Adverse Events

13.6.1 Establishing Diagnosis

Whenever possible, diagnoses should be given when signs and symptoms are due to a common etiology (e.g., dysuria, urinary nitrites should be reported as a urinary tract infection). If the diagnosis is not known, individual signs and symptoms should be assessed and recorded in the Adverse Event eCRF as separate AE. The Investigator (or qualified Subinvestigator) must assign the AE attributes listed in the following sections ([Table 2](#), [Table 3](#), and [Table 4](#)) and is responsible for ensuring their capture in the source documentation.

13.6.2 Assessment of Intensity

The Investigator will use clinical judgment as well as the guidelines laid out in the National Cancer Institute Common Terminology Criteria for Adverse Events (CTCAE), version 5.0 or most current version, to assess the intensity of each AE and SAE ([Table 2](#) and [Appendix 3](#)).

Table 2 Adverse Event Severity for Adverse Events

Grade*	Description
1	Mild; asymptomatic or mild symptoms; clinical or diagnostic observations only; intervention not indicated
2	Moderate; minimal, local or noninvasive intervention indicated; limiting age appropriate instrumental activities of daily living
3	Severe or medically significant but not immediately life-threatening, hospitalization or prolongation of hospitalization indicated; disabling; limiting self-care activities of daily living
4	Life-threatening consequences, urgent intervention indicated
5	Death related to adverse event

* Grade refers to the severity of the AE based on the National Cancer Institute CTCAE, version 5.0, and displays Grades 1 to 5 with unique clinical descriptions of severity for each AE.

The term “severe” is a measure of intensity, and a severe AE is not necessarily a “serious” AE.

When the intensity of an AE changes more than once a day, the maximum severity of the event should be entered into the Adverse Event eCRF. If the intensity changes over a number of days, these changes should be recorded separately (i.e., as having distinct onset dates).

13.6.3 Assessment of Causality to Study Drug

The Investigator should use clinical judgment as well as the guidelines in Table 3 to assess the relationship between study drug and AE.

Table 3 Adverse Event Relationship to Study Drug

Relationship to Study Drug	Comment
Related	There is clear evidence that the event is related to the use of study drug (e.g., confirmation by positive rechallenge test, if possible). Another etiology is considerably less likely.
Possible	The event cannot be explained by the patient’s medical condition, concomitant therapy, or other causes, and there is a plausible temporal relationship between the event and study drug administration.
Unlikely/Remote	An event for which an alternative explanation is more likely (e.g., concomitant medications or ongoing medical conditions) or the temporal relationship to study drug administration and/or exposure suggests that a causal relationship is unlikely. (For reporting purposes, Unlikely/Remote will be grouped together with Not Related.)
Not Related	The event can be readily explained by the patient’s underlying medical condition, concomitant therapy, or other causes, and therefore, the Investigator believes no relationship exists between the event and study drug.

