13.6.4 Assessment of Causality to Study Procedure

The Investigator should use clinical judgment as well as the guidelines in Table 4 to assess the relationship between study procedure and AE. Assessment of causality to study procedure should include causality to such items as EGD with biopsy or blood draw (as appropriate) or other.

Infusion-related reactions should not be assessed in relation to study procedure, only in relation to study drug.

Table 4 Adverse Event Relationship to Study Procedure

Relationship to Study Procedure	Comment
Related	There is clear evidence that the event is related to a study procedure.
Possible	The event cannot be explained by the patient's medical condition, concomitant therapy, or other causes, and there is a plausible temporal relationship between the event and a study procedure.
Unlikely/Remote	An event for which an alternative explanation is more likely (e.g., concomitant medications or ongoing medical conditions) or the temporal relationship to any study procedure suggests that a causal relationship is unlikely. (For reporting purposes, Unlikely/Remote will be grouped together with Not Related.)
Not Related	The event can be readily explained by the patient's underlying medical condition, concomitant therapy, or other causes, and therefore, the Investigator believes no relationship exists between the event and a study procedure.

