15.5 Analysis of Safety Endpoints

Adverse Events: All AE will be coded using the Medical Dictionary for Regulatory Activities (MedDRA) and will be classified by MedDRA system organ class and preferred term. Listings will include all AE collected on study. The summaries of AE will be based on TEAE, defined as an AE reported in the clinical database with a date of onset (or worsening) on or after the start date of the first intravenous infusion of the study medication.

Patient incidence (N and %) of TEAE will be summarized as follows:

- Overview of TEAE to include
 - Number (%) of patients who report at least one TEAE overall, by severity and by relationship
 - Number (%) of patients who report at least one serious TEAE
 - Number (%) of patients who report at least one TEAE leading to treatment discontinuation
 - Number (%) of patients who report at least one TEAE of special interest
- TEAE by preferred term
- TEAE by system organ class and preferred term

- TEAE by maximum severity, system organ class, and preferred term
- Drug-related TEAE by system organ class and preferred term
- TEAE leading to withdrawal by system organ class and preferred term
- Serious TEAE by system organ class and preferred term
- TEAE of special interest by system organ class and preferred term

Clinical Laboratory Assessments: Samples will be obtained for the clinical laboratory tests identified in Section 11.4, and laboratory tests to be summarized include blood chemistry, hematology, urinalysis, and ADA.

Descriptive statistics will be used to summarize laboratory results at baseline, each visit, and the change from baseline for each visit. In addition, shift tables will summarize the laboratory results relative to normal reference ranges at baseline and each post-baseline time point.

Vital Signs: Vital signs will be summarized at baseline, each visit, and change from baseline at each visit.

Physical Examination: New or worsening symptoms in the symptom-directed physical examinations will be included in the by-patient data listings.

Concomitant Medications: All medications will be coded using the most current World Health Organization Drug Dictionary. Concomitant medications will be summarized by Anatomical Therapeutic Chemical Class and preferred term.

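### Table 3 bars any competing cause under Possible, so events that drug and disease both plausibly explain have no proper level and are likely to drop out of the drug-related counts

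*Combined protocol and SAP*

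**What the plan says.** Section 13.6.3, Table 3, defines four levels of relationship to study drug:

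- **Related** has two conditions: "There is clear evidence that the event is related to the use of study drug", and "Another etiology is considerably less likely".
- **Possible** has two conditions. The timing in relation to dosing must be plausible, and no other cause may account for the event: "The event cannot be explained by the patient’s medical condition, concomitant therapy, or other causes".
- **Unlikely/Remote** is "An event for which an alternative explanation is more likely", or one whose timing argues against the drug. For reporting, it is pooled with Not Related.
- **Not Related** begins "The event can be readily explained by the patient’s underlying medical condition, concomitant therapy, or other causes" and adds that the Investigator, for that reason, holds that there is no relationship.

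The table is a guide to be used together with clinical judgment. Table 4 (Section 13.6.4) repeats the Possible definition for study procedures, with the timing clause "there is a plausible temporal relationship between the event and a study procedure". Its Related row asks only for clear evidence and has no clause on other causes.

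The Synopsis makes relationship to study drug part of the safety endpoint. Section 15.5 plans a TEAE overview by relationship and a table of "Drug-related TEAE by system organ class and preferred term", without saying which levels count as drug-related. Section 15 leaves full detail to a separate analysis plan.

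**The concern.** A middle level should hold the cases where the drug may be the cause but something else may be too. Possible, as worded, excludes exactly those cases.

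They matter in this trial. Section 2.4 lists abdominal pain, nausea, vomiting and diarrhea among the disease symptoms. Section 13.1 makes such symptoms adverse events once they worsen from baseline in severity or frequency. For those events the disease is always an available explanation. There is no randomization or blinding, and every patient receives AK002 (Sections 10.2 and 10.3). With no concurrent comparator rate, Investigator attribution carries much of the weight in separating drug from disease effects.

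At stake are the two summaries in Section 15.5 that use the scale. Under Section 13.7.2, the Investigator's causality call on a serious event also affects the timing of regulatory reporting.

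**Working it through.** The plan states no figure on this point, so the check reads the definitions side by side as logical conditions. Three features of an event decide the level: whether clear evidence points to the drug, whether the timing is plausible, and how any alternative cause compares with the drug. I take an event to be readily explained by another cause when that cause is at least as likely as the drug.

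With plausible timing, the literal text gives:

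| Alternative cause, compared with the drug | Clear evidence | No clear evidence |
|---|---|---|
| None | Related and Possible both fit | Possible |
| Considerably less likely | Related | no level fits |
| Somewhat less likely | no level fits | no level fits |
| Equally likely | Not Related only if the Investigator believes there is no relationship; otherwise none | same |
| More likely | Unlikely/Remote, or Not Related with that belief | same |

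Of the 5 × 2 = 10 cells, three have no level and two have one only if the belief condition is met. If readily explained were read to include less likely alternatives, the three empty cells would also become conditional on that belief; they would still not reach Possible. When the timing is implausible and there is no clear evidence, Unlikely/Remote always applies, so the gap concerns well-timed events only.

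Two cells show how Related and Possible compare. An unexplained, well-timed event without clear evidence is Possible but not Related. An event with clear evidence and a considerably less likely rival is Related but not Possible. Neither level contains the other: Possible is stricter on alternative causes, Related on evidence.

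In Table 4 the ordering problem does not arise, because its Related row has no alternative-cause clause. The gap does: a well-timed event without clear evidence, and with a rival cause that is equally or less likely, is not Related, Possible or Unlikely/Remote there either.

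For reporting, pooling Unlikely/Remote with Not Related leaves Related plus Possible as the implied drug-related group. An event in one of the gap cells enters that group only if the Investigator departs from the text.

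**The case against.** The strongest reply is that Table 3 is not an algorithm. Investigators apply judgment alongside it, and many would code an equally explained event as Possible whatever the definition says. That is fair, and nothing shows how sites actually behave. But Section 13.6.1 requires the Investigator to assign these attributes. Across about 60 centers, some following the text and some overriding it would make the counts inconsistent.

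The overlap with disease is also narrower than it first looks. Background disease symptoms at baseline level are not adverse events (Section 13.1). Reactions within 24 hours of the start of an infusion that the Investigator considers related to it are captured as one infusion-related reaction (Section 13.4) and are events of special interest (Section 13.3). What remains is mainly worsened symptoms not attributed to an infusion.

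Several stronger readings are tempting, and the documents do not support them:

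- A reader might infer that Possible is stricter than Related overall. It is not, because Related also needs clear evidence.
- A reader might infer that equally explained events are forced into Not Related. That level also requires a belief that no relationship exists, which an Investigator who sees an even balance does not hold. The text leaves a gap.
- A reader might infer a demonstrated bias in the drug's favour. Downward is the likely direction if the text is followed, but no data show that it is.
- A reader might infer that the stopping rules in Section 13.10 run on this scale. They speak of possible or probable relatedness, and Table 3 has no probable level. They are permissive and include grounds that do not depend on causality.

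**Conclusion.** The point holds as a defect in the wording of Possible. On alternative causes it sets a stricter test than Related, and the four levels do not cover well-timed events with a plausible competing cause. If sites follow the text, such events would likely stay outside the drug-related group, which would lower the TEAE-by-relationship and drug-related TEAE counts.

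The size cannot be estimated, because the documents give neither the frequency of such events nor the way sites grade them. Applying an assumed share to the planned maximum of about 183 patients (for example 0.10 × 183 = 18.3) only returns the assumption.

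All-causality, serious and special-interest TEAE summaries do not use the scale, and no formal inference is planned. The conclusion assumes that drug-related means Related plus Possible, which the pooling rule implies but Section 15.5 does not state.

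**What to change.** - **Tables 3 and 4, Possible:** say that the timing is plausible and the study drug (or procedure) cannot be excluded as a cause, even though the patient's condition, another treatment or something else could also account for the event. Unlikely/Remote then takes over once the alternative is the more likely one. With plausible timing, every row of the grid above then has a level.
- **Section 15.5:** state that drug-related means Related plus Possible.
- **Section 13.10:** reconcile its relatedness terms with the levels in Table 3.

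The cost is two table cells, one sentence and a reconciliation of terms. Under Section 17.1 this is a protocol amendment needing IRB approval and Investigator signature, and sites must be notified. No new data are collected. Drug-related percentages may look slightly less favourable. If events have already been graded under the present wording, the report should say which wording applied to them.

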13.6.4 Assessment of Causality to Study Procedure

The Investigator should use clinical judgment as well as the guidelines in Table 4 to assess the relationship between study procedure and AE. Assessment of causality to study procedure should include causality to such items as EGD with biopsy or blood draw (as appropriate) or other.

Infusion-related reactions should not be assessed in relation to study procedure, only in relation to study drug.

Table 4 Adverse Event Relationship to Study Procedure

Relationship to Study Procedure	Comment
Related	There is clear evidence that the event is related to a study procedure.
Possible	The event cannot be explained by the patient's medical condition, concomitant therapy, or other causes, and there is a plausible temporal relationship between the event and a study procedure.
Unlikely/Remote	An event for which an alternative explanation is more likely (e.g., concomitant medications or ongoing medical conditions) or the temporal relationship to any study procedure suggests that a causal relationship is unlikely. (For reporting purposes, Unlikely/Remote will be grouped together with Not Related.)
Not Related	The event can be readily explained by the patient's underlying medical condition, concomitant therapy, or other causes, and therefore, the Investigator believes no relationship exists between the event and a study procedure.

13.6.5 Action Taken

Action taken with respect to study drug will be categorized as none, study drug permanently discontinued (infusion is interrupted and is not restarted, and no subsequent infusions are given), study drug temporarily withdrawn (infusion is interrupted and is restarted, or the next infusion is still administered as planned), or other (specify).

Action taken with respect to study participation will be categorized as none, withdrawal from study participation, or other (specify).

Action taken with respect to treatment of an AE will be categorized as none, concomitant medication, concomitant procedure, or other (specify).

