13.9 Study Withdrawal Criteria

Patients will be discontinued from the study in the event that:

- Occurrence of an exclusion criterion, which is clinically relevant and affects the patient's safety, if discontinuation is considered necessary by the Investigator and/or Sponsor.
- Serum transaminases (ALT and/or AST) $>3 \times$ upper limit of normal (ULN) **and** total bilirubin $>2 \times$ ULN (confirmed by subsequent repeat) without an alternative explanation.
- Elevation of ALT and/or AST $>3 \times$ ULN (confirmed by repeat) with the appearance or worsening of symptoms thought by the Investigator to be potentially related to hepatic inflammation such as fatigue, nausea, vomiting, right upper quadrant pain or tenderness, fever, and rash.

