14.2 Early Discontinuation of Study Drug

A patient may be discontinued from study treatment at any time if the patient, the Investigator, or the Sponsor feels that it is not in the patient's best interest to continue. The following is a list of possible reasons for study treatment discontinuation:

- Patient withdraws consent.
- An AE that in the opinion of the Investigator results in it being in the best interest of the patient to discontinue study treatment.
- Protocol violation requiring discontinuation of study treatment.
- Participation in any other study during the duration of this study.
- Use of a non-permitted concomitant drug without prior approval from the Medical Monitor.
- Loss of ability to freely provide consent through imprisonment or involuntary incarceration for treatment of either a psychiatric or physical (e.g., infectious disease) illness.

If a patient is withdrawn from treatment due to an AE, the patient will be followed and treated by the Investigator or designee until the abnormal parameter or symptom has resolved or stabilized.

All patients who discontinue study drug treatment should be encouraged to continue on study and complete assessments and procedures according to [Table 1](#), if possible.

Reasonable attempts will be made by the Investigator to provide reasons for patient withdrawals. The reason for the patient's withdrawal from the study or all attempts to acquire such, will be specified in the source documents.

15. Statistical Methods and General Considerations

This section outlines the nature and rationale for the statistical methods to be used for analysis of the data from the study. A separate Statistical Analysis Plan will describe data handling and statistical techniques in full detail. The Statistical Analysis Plan will contain any modifications to the analysis plan described below.

All patient data will be listed. When appropriate, summary statistics of number of non-missing values, mean, median, standard deviation, minimum, and maximum will be computed for continuous variables, and summary statistics of number and percentage will be computed for categorical variables. No formal statistical inferences will be made. No imputation will be used for missing data.

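### The 'permanently discontinued' category in section 13.6.5 requires an interrupted infusion, so AK002 stopped for an AE outside an infusion has no named code and the 15.5 count of discontinuations could be incomplete

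*Combined protocol and SAP*

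**What the plan says.** Section 13.6.5 lists the actions that can be recorded against study drug for each AE. Apart from no action, there are three:

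- a permanent stop: "study drug permanently discontinued (infusion is interrupted and is not restarted, and no subsequent infusions are given";
- a temporary one, followed by the free-text option: "study drug temporarily withdrawn (infusion is interrupted and is restarted, or the next infusion is still administered as planned), or other (specify".

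A second field covers participation in the study, with the options "none, withdrawal from study participation, or other (specify".

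Section 14.2 lets treatment be stopped at any time. One listed reason is "An AE that in the opinion of the Investigator results in it being in the best interest of the patient to discontinue study treatment". It adds: "All patients who discontinue study drug treatment should be encouraged to continue on study".

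Section 15.5 plans an overview line, "Number (%) of patients who report at least one TEAE leading to treatment discontinuation", and a table, "TEAE leading to withdrawal by system organ class and preferred term". It names no source field for either and does not say whether the table's withdrawal is from drug or from study. Section 15.4 summarises completion, discontinuation from the study and the reasons for the latter. It plans no summary of reasons for stopping drug. Section 15 leaves data handling to a separate SAP, and the document under review contains no derivation for these outputs.

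**The concern.** The study gives a drug on 18 separate days and follows patients for AEs up to Extension Day 561. Much of what could end dosing will be recognised when no infusion is running. The category for permanent discontinuation is nevertheless described by what happens to an infusion in progress. A site that follows the text cannot use it for a stop decided between visits, while a site that follows the label alone will. The same clinical course can therefore receive different codes.

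Withdrawals due to AEs are a named safety endpoint in the synopsis, and longer-term tolerability is part of the objective in section 4. The proportion of patients who stop drug because of an AE is a main tolerability figure in an open-label extension. It should not depend on whether a drip was running when the decision was made.

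**Working it through.** The documents state no figure for AE-related discontinuation, so there is nothing to reproduce. The check applies the definitions to the possible courses and then asks what the planned outputs would show.

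**Step 1. Apply the 13.6.5 study-drug categories literally.**

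| Course | Category that fits |
|---|---|
| A. AE during an infusion; infusion stopped, no later doses | permanently discontinued |
| B. AE after an infusion has ended or between infusions; no later doses; patient stays on study | other (free text) |
| C. As B, but the patient leaves the study | other (free text) |
| D. Dose skipped for an AE; later doses given | other (free text) |

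B and C fail the permanent category because no infusion was interrupted. They fail the temporary category because nothing was restarted and no next infusion was given. 'None' is wrong because dosing ended. D fails the permanent category because later doses were given. It fails the temporary one because no infusion was interrupted and the next one did not go ahead as planned.

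Course B includes some infusion-related reactions. Section 13.4 counts reactions up to 24 hours from the start of infusion, and the minimum infusion times in section 9.6 are 4, 2 and 1 hours. A reaction can therefore begin after the infusion is over.

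**Step 2. Look for another record of the stop.**

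- Course C: the participation field shows withdrawal, and the reason enters the 15.4 summary.
- Course B: the participation field does not show withdrawal, and 15.4 has no discontinuation to report. Under section 14.1 a patient who completes visits through Day 561 is recorded as having completed the study. Of the fields and summaries described, only the 'other' free text ties the AE to the end of dosing.

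**Step 3. How much of the AE window lies outside an infusion?**

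- Minimum infusion time (section 9.6): 1 dose × 4 h + 5 doses × 2 h + 12 doses × 1 h = 26 h.
- Upper limit, from the rule that an infusion ends within 8 hours of preparation (section 9.5): 18 × 8 h = 144 h.
- AE window: 561 days × 24 h = 13,464 h.
- Share: 26 / 13,464 = 0.19% to 144 / 13,464 = 1.07%.

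About 99% of AE collection time is outside an infusion. This shows that courses B to D are not remote possibilities. It does not estimate the share of AE-related stops that fall there, since AEs may cluster around infusions.

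**Step 4. Effect on the 15.5 line.** Let D be the number of patients who stop drug for a TEAE, and b the share of them coded 'other' because the stop fell outside an infusion.

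- Count from the 'permanently discontinued' code alone: D × (1 − b).
- Count if the 'other' text is reviewed and correctly classified: D.

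The shortfall is D × b, which runs from zero to all of D. The documents give neither D nor b. If all 183 planned patients are dosed, each patient missed lowers the percentage by 1 / 183 = 0.55 points. Counting every 'other' entry as a discontinuation would not solve this, because 'other' also holds course D, where dosing resumed.

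**The case against.** The strongest reply has three parts.

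First, section 15.5 does not say that its count comes from this code, and the derivation is left to the SAP. If the free text is reviewed, the shortfall can be zero. This stands, and it is why the conclusion is conditional.

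Second, the parenthesis may be only an explanation for the infusion setting, with the absence of later infusions as its substance. Sites may well read it that way. But the text joins its conditions with 'and', and a definition that works only when part of it is ignored invites uneven coding.

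Third, no event is lost. All patient data are to be listed, and each AE enters the TEAE tables. Malignancies and parasitic or opportunistic infections are AESI with their own table, and serious events appear in the serious TEAE table. This also stands: what is at risk is the link between an event and the end of dosing.

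A reader might infer more than the text supports:

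- **That the study would miss delayed toxicity.** It would not, for the reason just given.
- **That the discontinuation count would be skewed toward infusion-type events.** This is not shown, because a stop for a reaction that begins after the infusion has ended fails the same definition.
- **That liver-test stops under section 13.9 would go unrecorded.** That section takes the patient off the study, so the participation field and the 15.4 reasons record them.

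**Conclusion.** The definition is too narrow as written. A permanent stop for an AE outside an infusion, and a dose skipped with dosing later resumed, have no named category. For patients who stop drug and remain on study, neither the participation action nor the 15.4 reasons supply the missing record. The count of TEAE leading to treatment discontinuation could therefore be too low or inconsistently coded.

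This rests on two assumptions: that at least some sites apply the definition literally, and that the count is taken from the 'permanently discontinued' code without review of the 'other' entries. A reader might infer that under-counting is certain, or attach a percentage to it. The documents support neither, because no source field is named and neither the number of AE-related stops nor their timing is given.

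The consequence is confined to a descriptive safety output. The protocol plans no formal inference, so sample size, power and error rates are unaffected. The correction is still worth making, because it protects a planned tolerability figure at little cost.

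**What to change.** 1. In section 13.6.5, define permanent discontinuation by its result: no further AK002 is given because of this AE, whether or not an infusion was in progress.
2. Add a category for a dose delayed or skipped because of an AE with later doses given.
3. In the SAP, derive the 15.5 treatment-discontinuation line from the redefined category. State also whether the withdrawal table refers to drug or to study, and which field feeds it.
4. Review 'other' entries already made and recode them to the new categories before the tables are run.

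This alters how a stop is recorded, not when drug is stopped. The cost is wording in the protocol and the eCRF completion guideline, an edit to the eCRF pick-list, a sentence or two in the SAP, and recoding of existing 'other' entries.
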